2.2 Study Objectives and Endpoints

Primary Objectives:

Pharmacokinetics

To characterize the local and systemic pharmacokinetics of one TFV IVR used continuously for 91 days

Safety

To evaluate the safety of one TFV IVR used continuously for 91 days

Secondary Objectives:

Adherence

To evaluate participant adherence to one TFV IVR used continuously for 91 days

Acceptability

To evaluate the overall acceptability of one TFV IVR used continuously for 91 days

Exploratory Objectives:

Adherence

To evaluate markers of ring use for the TFV IVR

Acceptability

To evaluate components of acceptability of ring use for the TFV IVR

Vaginal Microenvironment

To describe the genital microenvironment in HIV-uninfected participants during 91 days of continuous IVR use

Pharmacokinetics

To determine the anti-HIV activity in CVF and cervical tissue

To determine the anti-HSV-2 activity in CVF.

Primary Endpoints:

Pharmacokinetics

TFV levels in:

- o Plasma
- o Cervicovaginal fluid (CVF)
- o Rectal fluid
- o Cervical tissue

Tenofovir diphosphate (TFV-DP) levels in:

- o Cervical tissue

Safety

The proportion of participants with Grade 2 or higher genitourinary adverse event as defined by the Division of AIDS (DAIDS) Table for Grading the Severity of Adult and Pediatric Adverse Events, Corrected Version 2.1, July 2017, and/or Addendum 1 (Female Genital [Dated November 2007] Grading Table for Use in Microbicide Studies)

The proportion of participants with Grade 3 or higher adverse event as defined by the Division of AIDS (DAIDS) Table for Grading the Severity of Adult and Pediatric Adverse Events, Corrected Version 2.1, July 2017

Secondary Endpoints:

Adherence

Frequency of study IVR removal/expulsions (voluntary and involuntary) and duration without IVR in vagina (by self-report)

IVR use initiation and persistence (whether the IVR is in place when participants come to the clinic for their study visits)

Acceptability

Degree to which study participants liked or disliked using the IVR (by self-report)

Exploratory Endpoints:

Adherence

Plasma and CVF TFV levels

Residual drug levels in returned IVRs

Biomarkers of ring use

Acceptability

Self-reported attitudes about ring attributes, including dosing regimen and willingness to use IVR in the future

Interest/preference in a single vs. dual-purpose indication

The proportion of participants who find the study IVR to be at least as acceptable as other HIV prevention methods

Vaginal Microenvironment

Changes in microbiota and biomarkers

Impact of microbiota on TFV levels in tissue and plasma

Pharmacodynamics

Measures of HIV inhibition in CVF and cervical tissue

Measures of HSV-2 inhibition in CVF

2.3 Randomization

Participants were randomized in a 2:1 ratio to the active and placebo arms of the study. Study arm randomization was stratified by site to ensure balanced assignment of products at each site. In addition, biopsy collection was randomized to one of two biopsy schedule assignments. This schedule assignment was randomized and approximately balanced across sites and study product arms in a 1:1 ratio of Day 14 and Day 56 to Day 28 and Day 91. The randomization scheme has been generated and maintained by the MTN SDMC.

2.4 Blinding

This is not a blinded study. However, participants are not told their study product assignment.

2.5 Sample Size and Power

The proposed total sample size is approximately N=48 adult participants. The sample size is based upon the size of similar Phase 1 studies of vaginal microbicide products.

The statistical properties of the study are described using the probability of detecting pharmacokinetic (PK) concentrations among participants assigned to the active study product arm and the power to detect safety event differences between the study arms. For example, if the true rate of detection of PK concentrations among the 32 participants in the active arm is 99%, then the probability we will see 31 or more participants with detectable PK concentrations is 98%. Furthermore, if the true rate of a given safety event in the placebo arm is 12.5%, the sample size provides 90% power to exclude safety event rates greater than 57.5%.

Further details of the statistical properties for this study are described in section 10.4.1 of the protocol.

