### **10.4 Sample Size and Power Calculations**

#### **10.4.1 Primary Endpoints**

The proposed total sample size is approximately N=48 adult participants. The sample size is based upon the size of similar Phase 1 studies of vaginal microbicide products.

As a means to characterize the statistical properties of this study, Table 14 below presents the probability of observing thirty or more, thirty-one or more, or thirty-two participants with detectable PK levels (or a level above a specified threshold value) among the 32 participants in the active arm given a true event rate. For example, if the true rate of detection (or rate above a specified threshold) among participants using a ring is 99% then the probability we will see 31 or more participants with detectable PK levels is 96%.

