**Table 14: Analysis of PK Event Frequency**

“True” Event Rate (PK Detectable or above a specified threshold value)	P ( $\geq 30$ events   n=32)	P ( $\geq 31$ events   n=32)	P (32 events   n=32)
90%	0.37	0.16	0.03
95%	0.79	0.52	0.19
99%	>0.99	0.96	0.72

Table 15 below presents the probability of observing zero, one or more and two or more safety events among the 32 participants in the active arm given a true event rate. For example, if the true rate of a safety event among participants using a ring is 10% then the probability we will see 1 or more participants with this event is 97%.

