8.1 Pharmacokinetic Primary Endpoint

The proportion of participants with detectable drug levels in the active arm and the measured drug concentration levels will be summarized using descriptive statistics and graphics. Concentration of TFV will be summarized for plasma, cervicovaginal fluid (CVF), rectal fluid, and cervical tissue (biopsy) biological sample types and of TFV-DP concentrations in cervical tissue. Cervical tissue is collected at two time points: Participants are randomized to biopsy collection either at Visits 5 and 8 or Visits 6 and 9. Because of the limited time points per participant, not all the following described analyses will be possible for cervical tissue concentrations.

For concentrations of TFV that fall below the corresponding assay's lower limit of quantification (LLOQ), we will use a value equivalent to half the LLOQ. For CVF, rectal fluid and cervical tissue, the assay-level LLOQ will be adjusted for the sample weight to derive a weight-normalized LLOQ for each specimen sample.

The time to each sample collection will be calculated using the time of insertion of the first IVR at Enrollment, as recorded in the Ring Insertion and Removal eCRF, and the time of sample collection, as recorded in the PK results dataset from the Lab Data Management group.

TFV concentration in the sample types will be described using the following PK parameters: maximum observed concentration (C_{max}), area under the concentration-time curve ($AUC_{0-92\text{days}}$) from enrollment until the last collected sample (Day 92), and time to maximum observed concentration (T_{max}). AUC will be calculated using the trapezoidal method² on the observed times to sample collection. The geometric

mean, geometric coefficient of variation (CV%), median, interquartile range (IQR), minimum, and maximum will be reported for these PK parameters. The CV% will be calculated as $100 \times \sqrt{\exp(s^2) - 1}$, where s is the SD of the natural log-transformed values. The natural log transformation of the concentration values will be used. In addition, these same summary statistics will be used to describe TFV concentrations at each sample collection time-point.

The following tables and figures will be generated:

- Summary table of PK parameters by site and overall
- Summary table(s) of PK concentrations for each sample collection time point and sample type by site and overall

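### SAP 2.5 gives 98% for 31 or more PK detections out of 32 at a true rate of 99%; the exact value is 95.9%, and the protocol section it cites says 96%

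*SAP*

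**What the plan says.** SAP 2.5 (Sample Size and Power) gives two numerical properties of the design, one for PK and one for safety. The PK one is conditional: "if the true rate of detection of PK concentrations among the 32 participants in the active arm is 99" percent, "then the probability we will see 31 or more participants with detectable PK concentrations is 98" percent. The section then points elsewhere for the rest: "Further details of the statistical properties for this study are described in section 10.4.1 of the protocol".

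Protocol 10.4.1 (Primary Endpoints) carries the same example for the 32 active-arm participants. If the true rate "is 99% then the probability we will see 31 or more participants with detectable PK levels is 96" percent. The supporting table, "Table 14: Analysis of PK Event Frequency", shows 0.96 in the 99% row under 31 or more events with n = 32.

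On how the study was sized, SAP 2.5 says: "The sample size is based upon the size of similar Phase 1 studies of vaginal microbicide products".

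**The concern.** Both documents use n = 32, a true rate of 99% and a threshold of 31, and they are two points apart. A binomial tail with fixed inputs has one value, so at least one of them is wrong, and a reader who follows the SAP's own cross-reference meets the conflict at once.

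The practical risk is that the wrong figure is carried from the SAP into a study report or paper. It also makes the design look slightly more assured than it is. The chance of losing two or more participants to non-detection, when detection is truly 99%, is about twice what the SAP figure implies.

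**Working it through.** **Inputs.** n = 32 active-arm participants, true detection probability p = 0.99, threshold 31 or more (SAP 2.5 and Protocol 10.4.1, identical in both).

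**Step 1: reproduce the protocol's table.** With X ~ Binomial(32, p), the exact tails against Protocol Table 14 are:

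| p | P(X ≥ 30): exact / table | P(X ≥ 31): exact / table | P(X = 32): exact / table |
|---|---|---|---|
| 0.90 | 0.367 / 0.37 | 0.156 / 0.16 | 0.034 / 0.03 |
| 0.95 | 0.786 / 0.79 | 0.520 / 0.52 | 0.194 / 0.19 |
| 0.99 | 0.996 / >0.99 | 0.959 / 0.96 | 0.725 / 0.72 |

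All nine cells agree (the last is 0.72498, which rounds to 0.72). The protocol therefore used the exact binomial.

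**Step 2: the SAP's figure.**

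P(X ≥ 31) = 32 × 0.99^31 × 0.01 + 0.99^32 = 0.2343 + 0.7250 = 0.9593

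The SAP's 0.98 exceeds this by 0.98 − 0.9593 = 0.0207. The complement is P(X < 31) = 1 − 0.9593 = 0.0407, against the 0.02 that the SAP figure implies.

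**Step 3: a second check inside the protocol.** Thirty-one or more detections at 99% is the complement of two or more non-detections at 1%. Protocol Table 15 gives 0.04 for two or more events among 32 at a true rate of 1%, and 1 − 0.04 = 0.96.

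**Step 4: could 98% come from something else?**

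- *Another cell.* The 99% row reads >0.99, 0.96 and 0.72. None is 0.98.
- *Another rate.* With n = 32, a probability of 0.98 needs p ≈ 0.9932, not 0.99.
- *Another n.* At p = 0.99, at most one non-detection has probability 0.9798 with 22 participants. It is 0.9616 with 31 and 0.9166 with 48.
- *Poisson approximation.* With mean 32 × 0.01 = 0.32, e^(−0.32) × (1 + 0.32) = 0.9585.
- *Normal approximation.* Mean 31.68, SD √(32 × 0.99 × 0.01) = 0.563. Without continuity correction the result is 0.8865. With it, Φ((31.68 − 30.5)/0.563) = 0.982.

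Only the continuity-corrected normal lands near 98%. With 0.32 expected non-detections it is unsuitable, and neither document mentions it. The match may be coincidence; the documents do not show where 98% came from.

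**The case against.** The strongest reply is that nothing hangs on the number. It is offered as an example. The sample size was borrowed from comparable studies rather than derived from this probability. SAP 8.1 says of the PK endpoint that "the measured drug concentration levels will be summarized using descriptive statistics and graphics", so there is no success rule at 31 of 32. The SAP also reads as written after randomization: section 2.3 describes it in the past tense, and section 4 reports a monitoring review dated May 17, 2019. The sentence could therefore no longer influence the design. The correct value is one cross-reference away, and describing the gap as 4.1% against 2% makes a two-point slip sound larger than it is.

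All of that stands, and it fixes the weight of the point at the lowest level. It does not rescue the figure. The inputs are stated in full in the SAP sentence, no alternative reading gives 98%, and the cross-reference that limits the harm also exposes the disagreement. The SAP's other design figure, a rate of 57.5% at 90% power, agrees with Protocol 10.4.1 and Table 17. That suggests an isolated slip rather than a deliberate change of method.

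**Conclusion.** The SAP figure is wrong as printed. The correct value is 95.9%, or 96% rounded, so the SAP overstates it by 2.1 percentage points and contradicts the protocol section it cites. The calculation assumes only independent participants with a common detection probability of 99%, which is the model that reproduces the protocol's table. This is a minor correction to illustrative text. It raises no doubt about the sample size, the PK analysis or the protocol's own calculations.

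**What to change.** In SAP 2.5, replace 98% with 96%. The sentence then agrees with the text of Protocol 10.4.1, with Table 14 and with the complementary cell of Table 15. The cost is one number in the SAP. The protocol, sample size, analysis sets and planned analyses are unaffected. Any report text drafted from SAP 2.5 should be checked for the same figure.

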3. GENERAL DATA ANALYSIS CONSIDERATIONS

3.1 Analysis Set(s)

For the primary PK endpoint, all participants with concentration results from at least two sample collection timepoints will be included in the PK analysis set. For the primary safety endpoint and secondary

adherence endpoint, all participants with a study IVR inserted at any time during the trial will be included in the analysis set. For the secondary acceptability endpoint, all participants who completed question J2 of the product use end visit computer assisted self-interview (PUEV CASI) behavioral questionnaire will be included in the analysis set.

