### **Pharmacokinetics of vaginally administered tenofovir gel**

Studies of vaginal administration of TFV gel uniformly show  $C_{max}$  values for TFV in the blood plasma of around 4 ng/ml, equal to approximately 1/100 the systemic concentration after oral dosing. Concentrations of TFV-DP in PBMCs were undetectable or very low. While the exact level of genital tract exposure needed to prevent HIV is not known, TFV concentrations in undiluted aspirated cervicovaginal fluid (CVF) of >1000 ng/ml were associated with protection from HIV in the CAPRISA 004 study. Median values for TFV  $C_{max}$  in CVF aspirate in the CONRAD A04-095 and MTN-001 studies were well above the protective level from the CAPRISA 004 study and were also well above the concentration seen after oral dosing.

The CONRAD A04-095 study indicated that both single and multiple dose exposures of TFV gel led to high genital tract levels up to 24 hours post-dose. Concentrations of TFV-DP, the active metabolite, were detectable in about 40% of the vaginal tissue biopsy samples at concentrations similar to or higher than what is seen in PBMCs after oral exposure. MTN-001 showed that TFV-DP levels in tissue after vaginal dosing are 100 times higher than after oral dosing. High concentrations of TFV-DP were also seen in endocervical cells.

Additional studies that reported vaginal TFV PK data in non-pregnant women include MTN-011 and MTN-014. MTN-011 was a Phase 1 study that evaluated the effect of sex on PK of vaginally administered TFV 1% gel. Compared with dosing without sex, median TFV concentrations after sex decreased 72% and 78% ( $p < .001$ ) in CVF, 75% and 71% ( $p < .001$ ) in vaginal tissue, and 75% ( $p = .06$ ) and 55% ( $p < .001$ ) in cervical tissue with -1 hour and -24 hour dosing, respectively. Median concentration of TFV-DP also decreased significantly in cervical tissue with -1 hour dosing. BAT dosing resulted in drug levels at least as great as those in the absence of sex. MTN-014 was a Phase 1 cross-over study that evaluated the cross-compartment PK of TFV 1% gel (a reduced glycerin [RG] formulation) between the vagina and the rectum. After two weeks of daily administration of TFV 1% RG gel, TFV and TFV-DP levels were low or undetectable in cross-compartment tissue samples collected at 24 hours after administration of the last gel dose.

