## **Pharmacokinetics of Tenofovir IVR**

In CONRAD A13-128, all participants had plasma TFV levels below the limit of quantification (BLQ) at baseline. The plasma TFV levels rose to a median (IQR) of 2.3 (1.7-3.3) ng/mL prior to IVR removal, which is well within the low range expected from topical dosing of TFV vaginal gel as compared to oral dosing of TFV, and fell to BLQ values within 24 hours of IVR removal. These data support that after 16-18 days of IVR use, plasma TFV levels remain in the low range expected for topical dosing. TFV concentrations in CV aspirate exceeded 1,000,000 ng/mL (n=38) during IVR use and 1,000 ng/mL at 24 hours post removal, suggesting that the IVR delivers consistent TFV concentrations similar to or exceeding peak concentrations achieved with TFV 1% gel. TFV and TFV-DP concentrations in vaginal tissues during IVR use and post IVR removal were also consistent with ranges found after dosing of TFV vaginal gel in women.

In CONRAD A15-140, concentrations of TFV in plasma were greater following oral treatment with Truvada than following TFV IVR, while concentrations of TFV and TFV-DP in cervical and vaginal tissue were greater following TFV IVR use than following Truvada. TFV and TFV-DP concentrations met established concentrations in tissue after 14 days of IVR use. TFV concentrations in the plasma was low as expected with topical administration. Median TFV concentrations in tissue were  $>10^4$  ng/g and median TFV-DP concentrations in tissue were  $>10^6$  fmol/g.

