### **6.4.4 Retrieval of Used Study Product**

Study participants will be instructed to return for IVR removal at the PUEV/Early Termination Visit. If the participant has removed the IVR and it is not returned at the PUEV/Early Termination Visit, site staff members will make every effort to encourage

participants to return the IVR as soon as possible (optimally within 5 working days). Attempts by study staff to retrieve the IVR from the participant must be documented.

When product use is permanently discontinued for HIV infection or pregnancy, the IVR must be retrieved (optimally within 24 hours of site awareness) and returned to the clinic (see Table 3 below). Additional IVR retrieval specifications in response to discontinuations for other reasons, or IoR discretion, can be found in Table 3. Study product retrieval may occur either by the participant returning the IVR to study staff within the specified timeframe or attempts should be made by study staff to contact the participant and retrieve the IVR as soon as possible. If the IVR is not returned within the time frames outlined below, the MTN-038 PSRT must be notified.

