**Table 3: Retrieval of IVR**

Reason for Ring Removal	Timeframe for Study Product Retrieval
Permanent discontinuation or temporary hold due to potential HIV infection or pregnancy	Within 24 hours
Permanent discontinuation for any other reason or IoR discretion	Within 5 working days
Temporary hold for any other reason with expected duration of greater than 7 days	Within 7 working days

If there is a product hold, expulsion (i.e., ring removed and cannot be reinserted) or an extended period of time that the ring is removed, the MTN-038 PSRT should be notified. The PSRT will evaluate each reported event to determine if the ring should be reinserted, if a new ring should be dispensed, or if the participant should discontinue product use. See [Section 9](#) for additional information related to product holds. Additional guidance regarding ring expulsions and/or removals will be provided in the SSP.

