### **9.3 General Criteria for Temporary Hold and Permanent Discontinuation of Study Product**

A participant will be permanently discontinued from IVR product use by the IoR/designee for any of the following reasons:

- Acquisition of HIV-1/2 infection; such participants will not resume product use at any time. The study IVR must be held beginning immediately upon recognition of the first reactive rapid HIV test.
- Allergic reaction to the IVR
- Pregnancy
- Breastfeeding
- Non-therapeutic injection drug use

A participant will be temporarily discontinued from IVR product use (a product hold will be implemented) by the IoR/designee and a PSRT query submitted for any of the following reasons:

- Reported use of PEP for HIV exposure
- Reported use of PrEP for HIV prevention
- Use of heparin, Lovenox®, warfarin, Plavix® (clopidogrel bisulfate), or other anticoagulant
- Any clinical study product hold lasting more than 7 days
- Participant is unable or unwilling to comply with required study procedures, or otherwise might be put at undue risk to their safety and well-being by continuing product use, according to the judgment of the IoR/designee. (May result in temporary hold or permanent discontinuation)

The IoR/designee must consult the PSRT once the temporary hold is initiated. Together, the IoR/designee and the PSRT will discuss resuming product use, continuing the temporary hold, or progressing to permanent discontinuation.

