9. SECONDARY ENDPOINT ANALYSES

9.1 Adherence Secondary Endpoint

To assess participant adherence to the IVR, the proportion of participants who reported keeping the study IVR inserted at all times during the 91 days will be calculated along with a 95% confidence interval, using the exact Pearson-Clopper method, and these proportions will be formally compared using Fisher's exact test. Adherence will be calculated using the self-reported IVR outages from the Ring Adherence eCRF and clinician-reported outages reported on the Study Termination, the Discontinuation of Study Product, the Product Hold Log, and the Ring Insertion and Removal eCRFs. Clinician-initiated IVR removals for the purpose of clinical examination will be excluded from consideration during product adherence analysis.

For participants who were not fully adherent, the number, median, and IQR of the duration of self-reported removal/expulsion events will be reported. Additionally, the median and IQR of the cumulative time during the study period when the study IVR was outside the vagina will be calculated. No formal statistical comparisons will be performed.

Additional summaries of the number and proportion of participants who had the vaginal ring in place at the start of the visit, who had the ring removed at the visit, who had a ring inserted at the visit, and the reasons for removals from the Ring Insertion and Removal eCRF will be tabulated by arm. The following information collected on the Ring Adherence eCRF will be tabulated for all follow-up visits, overall and by arm: the total number of times that the participant had the vaginal ring out; the number of times that the participant had the vaginal ring out for more than 12 hours continuously (grouped in following categories: 0, 1, 2, 3 or more), the longest number of days in a row the vaginal ring was out; the number and proportion of participant visits where the ring was removed; the number and proportion of participant visits where the ring came out on its own; the number and proportion of participant visits reporting the different reasons why the vaginal ring was removed and the reasons why the vaginal ring came out on its own. No formal statistical comparisons will be performed.

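### SAP 3.1 and 8.1 summarise PK results without regard to ring status, although the objective is one ring used continuously for 91 days

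*SAP*

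**What the plan says.** The primary PK objective, in Protocol 3.1 and SAP 2.2, concerns one ring in continuous use for 91 days. SAP 3.1 defines the PK set by a count of results: "all participants with concentration results from at least two sample collection timepoints will be included in the PK analysis set". SAP 8.1 gives Cmax, Tmax, AUC over 92 days and the proportion with detectable drug, and adds that "these same summary statistics will be used to describe TFV concentrations at each sample collection time-point". Sample times run from insertion of the first ring at Enrollment, and values below the LLOQ are set to half the LLOQ. Neither section mentions ring status or co-medication, and Protocol 10.7.2 adds no rule.

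The protocol provides for time off the ring:

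- Section 6.4.4 (Table 3 and the text below it) covers holds, expulsions and extended removals: "The PSRT will evaluate each reported event to determine if the ring should be reinserted", or a new ring dispensed, or use discontinued.
- Section 6.4.4 also covers the end of use: "If the participant has removed the IVR and it is not returned at the PUEV/Early Termination Visit".
- Sections 9.3 and 9.6 set out temporary holds. One trigger is "Reported use of PrEP for HIV prevention".

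Section 7.5.3 drops tenofovir sampling after permanent discontinuation. It sets no such rule for temporary holds, removals or expulsions.

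Ring status is recorded. SAP 9.1 tabulates participants "who had the vaginal ring in place at the start of the visit", together with removals and outages, and SAP 10.1 tabulates holds. None of this is linked to the PK analysis.

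**The concern.** A concentration measured with the ring out says little about release from a ring in continuous use. If such a sample is summarised at its nominal visit, non-wear and low release cannot be told apart. The geometric mean falls, the CV grows, and the hypothesis that drug will be measurable in every participant (Protocol 10.3) can appear to fail because a ring was out.

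Day 91 is a particular case. A woman who arrives with the ring already out could contribute a sample filed as the pre-removal one when it is in fact post-removal.

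Plasma reflecting oral tenofovir would push the other way. That case should be rare.

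**Working it through.** **The plan's own figures.** This point disputes no printed number. The nearest is the 96% chance of at least 31 of 32 detectable when the true rate is 99% (Protocol 10.4.1). It reproduces: 0.99^32 + 32 × 0.99^31 × 0.01 = 0.725 + 0.234 = 0.959. SAP 2.5 prints 98% for the same quantity, a separate inconsistency with no bearing here.

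**Inputs from the documents**
- 32 active-arm participants (Protocol 10.1).
- Plasma before ring removal: median 2.3 ng/mL, IQR 1.7-3.3, after which levels "fell to BLQ values within 24 hours of IVR removal" (Protocol 2.4.3).
- Cervicovaginal aspirate: above 1,000,000 ng/mL during use and above 1,000 ng/mL at 24 hours after removal (same section).
- Half-LLOQ substitution and CV% = 100 × √(exp(s²) − 1) (SAP 8.1).

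**Assumptions, not in the documents**
- 2 of 32 samples at a visit are ring-out, so p = 0.0625.
- Plasma LLOQ is 0.1 to 1 ng/mL.
- On-ring plasma is log-normal, and ring-out plasma is below the LLOQ.

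**Plasma.** On-ring log-SD s = ln(3.3/1.7)/1.349 = 0.492, so CV = 52%. Let d = ln((LLOQ/2)/2.3). The geometric mean ratio is exp(p·d), and the log variance is (1 − p)s² + p(1 − p)d².
- LLOQ 0.1: d = −3.83, ratio 0.787 (−21%), variance 1.086, CV 140%.
- LLOQ 0.3: d = −2.73, ratio 0.843 (−16%), variance 0.663, CV 97%.
- LLOQ 1.0: d = −1.53, ratio 0.909 (−9%), variance 0.363, CV 66%.

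With an n − 1 divisor the CVs are 143%, 98% and 67%. One ring-out sample instead of two lowers the geometric mean by 5-11%; five lower it by 21-45%.

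**Median.** With two values moved to the bottom, the overall median sits at the (0.5 − 0.0625)/0.9375 = 0.467 quantile of the on-ring distribution (z = −0.084). The ratio is exp(−0.084 × 0.492) = 0.96, a fall of about 4%.

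**CVF.** Taking the two thresholds as if they were values, the geometric mean ratio is (1,000/1,000,000)^(2/32) = 0.649, a fall of about 35%.

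**Detectable proportion.** If it is computed per visit, two ring-out results below the LLOQ turn 32/32 into 30/32. Protocol Table 16 gives lower 95% bounds of 89% and 79% for these.

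**AUC.** Plasma is not sampled at Day 42, so a Day 56 value governs the trapezoids from Day 28 to Day 91, which is 63 of 91 days. Take a flat on-ring level c and a ring-out Day 56 value v. Keeping v removes 31.5 × (c − v) from 91 × c. With c = 2.3 and v = 0.05 to 0.5 this is 34% to 27% of that woman's AUC, even if the ring was out for one day in 91 (about 1%). Deleting v draws a straight line across the gap and credits full exposure to time without a ring. Neither gives her on-ring AUC.

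**The case against.** The strongest reply is that contamination is inferred from silence. SAP 3.1 says which participants enter the set, not which samples are summarised. No section states that a woman on a temporary hold is still sampled; the closing words of the procedure list in Protocol 7.5.3, which mention a prior hold, are ambiguous. Instructions on PK sampling, expulsions and removals are deferred to the SSP Manual, which is not available here. For permanent discontinuation, the management team may omit samples not expected to be analysable. Participants are told to return for removal at the Day 91 visit, and an outage matters only if it spans or shortly precedes a sample. All of this stands. A reader might infer that ring-out samples are certain to be in the data, or that sampling through holds is mandated. The documents support neither.

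The SAP also reports medians, IQRs and ranges and plots every participant, so outlying values would be visible and the median is robust. That limits the harm but gives no rule for interpreting those values. If the detectable proportion means ever detectable, which SAP 8.1 does not settle, one ring-out sample changes nothing.

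A reader might also infer that oral tenofovir threatens the plasma results. PrEP and PEP are prohibited (Protocol 6.6), recent use is an exclusion (5.3), and reported use triggers a hold. The statement "equal to approximately 1/100 the systemic concentration after oral dosing" compares oral dosing with gel, whose peak is around 4 ng/mL, so it cannot be read as a multiple of the ring level. I put no size on this case.

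Finally, an all-samples summary is legitimate. Plasma and CVF levels are also exploratory adherence endpoints, which need every sample. That argues for keeping it beside an on-ring summary, not in place of one.

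**Conclusion.** The gap holds: the primary PK summaries are not tied to ring status, while the objective is continuous use and the protocol foresees time off the ring. Any ring-out sample that is collected would enter the scheduled on-ring rows and the detectable proportion.

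The illustrated size is moderate for plasma and larger for CVF, and small for the median. The plasma and CVF figures rest on an assumed two ring-out samples at one visit. The plasma range also rests on an assumed LLOQ, and the CVF figure on reading thresholds as values. Both describe levels within or at about 24 hours after removal, so they suit outages of roughly a day. The actual effect depends on how many such samples occur, which the documents cannot show. This should be fixed in the SAP; it does not invalidate the design.

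**What to change.** In SAP 8.1:

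1. Derive a sample-level on-ring flag from the Ring Insertion and Removal, Ring Adherence and Product Hold Log eCRFs and the concomitant medication data. The flag requires the ring in place at the start of the visit, no documented outage within a prespecified window before the sample, and no reported PrEP or PEP. The window is needed because a ring reinserted just before the visit would otherwise pass.
2. Report time-point concentrations and the detectable proportion for flagged samples as the summary that answers the continuous-use objective, beside the all-samples summary. List the samples left out and the reason, and say whether detectability is per visit or ever.
3. Do not compute AUC by deleting off-ring samples and interpolating. Report AUC, Cmax and Tmax for all participants, and again for those with no documented outage or oral tenofovir use.
4. Keep the 4-hour post-removal and Day 92 samples at their own time points, since they are off-ring by design, but time them from actual removal.

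The cost is SAP wording and one derived variable; no new data are needed. The downside is a smaller n at affected visits. The rule should be fixed before concentrations are reviewed, because SAP 2.4 states that the study is not blinded and later exclusions would be open to challenge.
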